MAIN STUDY PROCEDURES	 Randomisation 1 Multi-parametric MRI compared to biparametric MRI Randomisation 2 Targeted biopsy performed using image-fusion targeted and systematic biopsies compared to visual-registration targeted and systematic biopsies in patients with visible suspicious finding on either bpMRI or mpMRI. Duration of follow-up: For up to 12 weeks after enrolment.
OUTCOME MEASURES (PRIMARY ENDPOINTS)	
Randomisation 1	Proportion of clinically significant cancers, defined as any amount of Gleason >/=3+4 (ISUP Grade Group >/=2) on biopsy, detected in the randomised population of patients at risk.
Randomisation 2	Proportion of clinically significant cancers, defined as any amount of Gleason >/=3+4 (ISUP Grade Group >/=2) on biopsy, detected in the randomised population of patients biopsied for a suspicious MRI.
OUTCOME MEASURES (SECONDARY ENDPOINTS)	
	Proportion recommended for biopsy in randomised arm Proportion actually biopsied in each randomised arm

Proportion diagnosed with clinically insignificant prostate cancer (defined as any Gleason 3+3=6 [ISUP Grade Group 1])
Proportion of clinically significant and insignificant cancers using other histological definitions of clinical significance - PROMIS 1 and 2 - any Gleason >/=4+3 [ISUP Grade Group >/=3] - Gleason >/=3+4 [ISUP grade Group >/=2] or any Gleason 3+3 [ISUP Grade Group 1] of >/=6mm - Gleason >/=3+4 [ISUP grade Group >/=2] with >/=10% pattern 4 OR presence of cribriform pattern OR presence of intraductal components
Detection rates for each randomised group of known prognostic risk categories. These are D'Amico, National Comprehensive Cancer Network (NCCN) and Cambridge Prognostic Groups (CPG).
Adverse events and patient reported outcomes
Outcomes by centre stratified by size and type of MRI scanner, route of biopsy and amount of systematic sampling.
Healthcare resource utilisation, costs and cost- effectiveness of using fastMRI compared to mpMRI and image-fusion compared to cognitive targeted biopsies
Consent for linkage to national databases to collect medium and long-term outcomes including new diagnostic tests, prostate cancer diagnoses and treatments, deaths and prostate cancer deaths

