- Characteristics of cancer in targeted versus systematic biopsies and by MRI score, PSA, PSA density, age, ethnicity, family history and history of prior prostate biopsy with a multivariable evaluation to determine patients might avoid systematic sampling in future.
- External validation of the Imperial RAPID Risk Score (MRI+) and Imperial RAPID Risk Score (Systematic+) within each randomised group of the IP7-PACIFIC study
- Impact of prostate biopsy in each randomised group on patient reported outcomes and patient reported experience measures using an updated version of the Prospective cohort study (Prostate Biopsy Effects: ProBE) questionnaire [Rosario et al, 2012] and the EQ-5D-5L health-related quality of life questionnaire, and stratified by type of biopsy (transrectal vs. transperineal; for transperineal biopsy, limited systematic vs. sectoral systematic.
- Analysis of biopsy rates and detection of cancer (by all histological thresholds) as well as patient reported outcomes and experience measures in randomised group will be conducted by centre using centre size. MRI scanner type (1.5Tesla vs. 3.0Tesla), type of biopsy route used (transrectal vs. transperineal), number of systematic biopsy taken (limited systematic vs. extended systematic biopsy), type of analgesia/anaesthetic (local anaesthetic, sedation or general anaesthetic) as additional stratification factors.

Definitions of clinical significance on biopsy

As well as the primary outcome definition of any amount of Gleason 3+4 or greater on any one or more biopsy cores, we will also use the following histological thresholds:

i) any amount of Gleason 4+3=7 or more

ii) any amount of Gleason >/=4+3 OR Gleason 3+3=6 of >/=6mm (PROMIS definition 1)

iii) any amount of Gleason >/=3+4 OR Gleason 3+3=6 of >/=4mm (PROMIS definition 2)

iv) any amount of Gleason >/=3+4 OR Gleason 3+3=6 of >/=6mm

v) Gleason 3+4=7 with >10% pattern 4 OR cribriform pattern OR a ductal component

Health economic

- Incremental cost per clinically significant cancer detected and incremental cost per correct diagnosis.
- Modelled healthcare resource utilisation, NHS and PSS costs and incremental cost per QALY of using bpMRI compared with mpMRI. The model will incorporate the costs and impacts of potential changes in rates of biopsy and cancer treatment with different types of MRI.

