The histological report will evaluate the following aspects for each target and each location of systematic biopsies carried out according to Royal College of Pathology (UK) guidance [Royal College of Pathology Guidelines, 2016]: number of biopsies, number positive for cancer, core length in mm, cancer presence, maximum cancer core length in mm (where continuous and discontinuous numbers are given, for the purpose of analysis, the continuous number will be used), primary, secondary and highest Gleason grade, percent pattern 4 and presence of cribriform pattern when Gleason 3+4, perineural invasion/lymphovascular invasion/intraductal components/neuroendocrine differentiation; and vii) other features (high grade prostatic intraepithelial neoplasia/atypical acini/inflammation/atrophy). See Biopsy Reporting SOP.

Definition of clinically significant prostate cancer on histology

We know that some prostate cancers are clinically significant, and that other prostate cancers are clinically insignificant. Whilst there is still some uncertainty about exactly what entails clinical significance, particularly with respect to whether patients diagnosed with low volume Gleason 3+3 or Gleason 3+4 cancer should be on active surveillance, most physicians, researchers and guideline panels agree detection of Gleason >/=3+4 (ISUP grade Group >/=2) is the key target condition for any screening or diagnostic pathway. As a result, this is the primary histological threshold we will measure.

There is also acknowledgement that a low amount of cancer or low percent pattern 4 is perhaps not as aggressive. So, whilst the primary outcome measure will be the detection of any Gleason >/=3+4, there are important secondary definitions of clinical significance that we will measure as well. These definitions will incorporate the wide and divergent views on clinical significance but incorporate evidence on the amount of pattern 4 and maximum cancer core length as being significant elements [26-30]. These definitions will be:

- any amount of Gleason 4+3=7 or more
- any amount of Gleason >/=4+3 OR Gleason 3+3=6 of >/=6mm (PROMIS definition 1)
- any amount of Gleason >/=3+4 OR Gleason 3+3=6 of >/=4mm (PROMIS definition 2)
- any amount of Gleason >/=3+4 OR Gleason 3+3=6 of >/=6mm (PROMIS definition 3)

- any amount of Gleason 3+4=7 with cribriform pattern or a ductal component or >/=10% pattern 4 or any Gleason >/=4+3 [van Leenders et al, 2020].

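### Secondary definition v of clinically significant cancer is worded three ways, and section 2.4 leaves out Gleason 4+3 and above; definition ii is not ordered by grade and needs checking against its source

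*Protocol*

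**What the plan says.** The secondary thresholds appear in three places in the protocol.

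- **Section 2.4, Definitions of clinical significance on biopsy.** The list is introduced by "As well as the primary outcome definition of any amount of Gleason 3+4 or greater on any one or more biopsy cores", so the primary rule counts every cancer of Gleason 3+4 or above. Definition v is "v) Gleason 3+4=7 with >10% pattern 4 OR cribriform pattern OR a ductal component".
- **Section 5, Definition of clinically significant prostate cancer on histology.** The matching item is "any amount of Gleason 3+4=7 with cribriform pattern or a ductal component or >/=10% pattern 4 or any Gleason >/=4+3".
- **Trial Summary, secondary outcome measures.** The matching item is "Gleason >/=3+4 [ISUP grade Group >/=2] with >/=10% pattern 4 OR presence of cribriform pattern OR presence of intraductal components".

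Definition ii is "ii) any amount of Gleason >/=4+3 OR Gleason 3+3=6 of >/=6mm (PROMIS definition 1" in section 2.4 and has the same wording in section 5. The Trial Summary only names it. Definition iv is "iv) any amount of Gleason >/=3+4 OR Gleason 3+3=6 of >/=6mm" in section 2.4; section 5 states the same criterion but labels it PROMIS definition 3, a label found nowhere else.

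Among the items in the histology report, section 5 lists intraductal components. For further detail it points to a Biopsy Reporting SOP, which is not shown.

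**The concern.** An endpoint should have one rule, and a rule for significance should not turn from yes to no as grade rises. Definition v fails the first test across the three lists and the second within section 2.4. Definition ii fails the second in both full lists.

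The secondary thresholds are used widely. Sections 2.2 and 2.4 apply them to detection by arm, to the MRI-score and risk-factor analyses, to Likert against PIRADS, to 4 against 6 targeted cores and to the analyses by centre. Because insignificant cancer is also reported under each alternative threshold, a 4+3 cancer that drops out of definition v would be counted as insignificant under that threshold, so detection and overdiagnosis would both be misstated.

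This is not a detail left to the statistical analysis plan. The protocol fixes the definition and contradicts itself, so whoever writes the analysis could follow any of three texts.

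**Working it through.** There is no stated figure for this point to reproduce. Each wording was treated as a yes/no rule and applied to the same set of cases. The section 2.4 line can be read in two ways: (a) all qualifiers attach to Gleason 3+4; (b) the cribriform and ductal features stand alone.

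**Definition v** (core length plays no part; feature = cribriform or ductal/intraductal)

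| Case | 2.4 (a) | 2.4 (b) | Section 5 | Summary |
|---|---|---|---|---|
| 3+4, 5% pattern 4, no feature | no | no | no | no |
| 3+4, 10% pattern 4, no feature | no | no | yes | yes |
| 3+4, 20% pattern 4, no feature | yes | yes | yes | yes |
| 4+3, 60% pattern 4, no feature | no | no | yes | yes |
| 4+3, 60% pattern 4, feature present | no | yes | yes | yes |
| 4+4, 100% pattern 4, no feature | no | no | yes | yes |
| 4+4, 100% pattern 4, feature present | no | yes | yes | yes |

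Three differences follow.

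1. *High grade.* Under both readings of section 2.4, a 4+3 or 4+4 cancer with no feature is not significant, while a 3+4 with 20% pattern 4 is. The other two texts count all of them.
2. *Cut-off.* A 3+4 cancer at exactly 10% pattern 4 with no feature changes class between section 2.4 and the other two texts.
3. *Feature.* Sections 2.4 and 5 rely on a ductal component; the Trial Summary and the listed report items say intraductal. The table treats these as one feature. If the form separates them, section 5 and the Trial Summary can also disagree, for a 3+4 with under 10% pattern 4.

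**Definition ii**

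| Case | 3 mm | 8 mm |
|---|---|---|
| 3+3 | no | yes |
| 3+4 | no | no |
| 4+3 | yes | yes |

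At 8 mm the answer runs yes, no, yes as grade rises.

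**Illustrative size for definition v.** Inputs from section 8.1: 38% detection at 3+4 or above in randomisation 1; 55% and 65% in the arms of randomisation 2, midpoint (55 + 65)/2 = 60%. Assumption, not in the protocol: 30-45% of these cancers are 4+3 or higher. Points lost = detection × share, under reading (a):

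- Randomisation 1: 0.38 × 0.30 = 0.114; 0.38 × 0.45 = 0.171. About 11-17 points.
- Randomisation 2: 0.60 × 0.30 = 0.18; 0.60 × 0.45 = 0.27. About 18-27 points.

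Under reading (b) the loss is smaller, because high-grade cancers with a feature still count.

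**Sample size.** With 38% in both arms, a 5-point margin, one-sided 5% and 90% power, n = (1.645 + 1.282)² × 2 × 0.38 × 0.62 / 0.05², which gives 1,615 per arm, as in section 8.1. No secondary threshold enters it.

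**The case against.** The strongest reply is that this is a wording slip already corrected elsewhere in the protocol. Section 5 is the fuller text, cites a source and includes 4+3 and above. The Trial Summary agrees with it on every case tabulated. Definition i in section 2.4 separately counts every cancer of 4+3 or more, so high-grade disease is reported in any event. The same rule would also apply to both arms. All of this is fair, and it limits the point to a correction of secondary endpoints. It does not remove it: section 2.4 is the endpoint section, and equal application to both arms does not make the wrong set of cancers the right one.

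A reader might be tempted to infer more, and the documents do not support it.

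- *That the trial means to treat 4+3 as insignificant.* Section 5, the Trial Summary and definition i all point the other way.
- *That definition ii is wrong and should apply the 6 mm rule to 3+4 as well.* It carries the name of an external definition whose text is not in the protocol. The lack of grade order is a reason to check it, not grounds for rewriting it unseen.
- *That patients with 3+3 in one core and 3+4 in another are counted as both insignificant and significant.* The phrase any Gleason 3+3 allows this if read literally. But the Trial Summary equates it with ISUP Grade Group 1, significance is decided on one or more cores, and highest grade is recorded, which together suggest classification by highest grade. Stating so would be tidier, no more.
- *That a ductal component is not recorded.* The Biopsy Reporting SOP is not shown, so this cannot be settled from the protocol.

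**Conclusion.** The point holds in limited form. Definition v has three wordings that do not form one rule, and the one in section 2.4 excludes Gleason 4+3 and above, at least where there is no cribriform or ductal feature. That follows from the text under either reading and needs no assumption. Definition ii is consistent between the two full lists but not ordered by grade; whether that is a transcription error cannot be decided from the protocol.

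The figures of 11-17 and 18-27 points are upper illustrations and not expected losses. They need the assumed grade mix, the reading in which every qualifier attaches to 3+4, and an analyst who follows section 2.4 against the other two texts. No size can be put on definition ii. A reader might infer that the main results are at risk; they are not, since the primary definition is the same throughout and the sample size does not depend on these thresholds.

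**What to change.** 1. Replace the section 2.4 and Trial Summary wording of definition v with the section 5 rule: Gleason 4+3 or higher, or Gleason 3+4 with at least 10% pattern 4, cribriform pattern or the ductal/intraductal feature. Use one cut-off throughout, and whichever of ductal or intraductal the histology form records.
2. Check definition ii against the cited source definition. Correct it in both lists if it was mistranscribed; if it was not, say that the lack of grade order is as published.
3. Give definition iv the same label in every list.
4. Optionally, state that clinically insignificant means that 3+3 is the highest grade found in the patient.

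The cost is wording in three places, plus a check that the database derivations and analysis programs follow the agreed text. Grade, percent pattern 4, cribriform pattern, intraductal components and core length are already listed as reported items in section 5, so no new procedure or visit is needed.

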2.3 Primary Endpoint

Randomisation-1: bpMRI versus mpMRI

Proportion of clinically significant cancers, defined as any amount of Gleason >/=3+4 (ISUP Grade Group >/=2) on biopsy, detected in the randomised population of patients at risk.

Randomisation-2: Visual-registration targeting versus image-fusion targeting

Proportion of clinically significant cancers, defined as any amount of Gleason >/=3+4 (ISUP Grade Group >/=2) on biopsy, detected in the randomised population of patients biopsied for a suspicious MRI.

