2.4 Secondary Endpoints

Clinical

In each of the randomised groups, secondary outcomes are:

- MRI and biopsy-related adverse events and serious adverse events
- The proportion of patients advised to undergo a needle biopsy and the proportion of
 patients undergoing a prostate biopsy after MRI. We will document common reasons for
 patients who are advised to undergo a biopsy who decline and reasons for patients who
 are advised against a needle biopsy who still choose to have a biopsy. We shall record
 the number of patients with a non-suspicious bpMRI/mpMRI that are recommended for
 biopsy and the types cancers subsequently detected.
- The proportion of patients diagnosed with clinically insignificant prostates cancers, defined as any Gleason 3+3=6 on needle biopsy carried out after MRI. These will also be stratified by MRI score, presence of clinical risk factors and whether the biopsy was carried out on clinician recommendation or patient choice.
- The proportion of patients diagnosed with clinically significant and clinically insignificant prostate cancers using other histological thresholds, on prostate biopsy carried out after MRI. Similarly, as above, we will also evaluate these proportions by MRI score at patient and lesion level (on a scale of 1 to 5) and by presence or absence of clinical risk parameters.

- The proportion of patients diagnosed with clinically significant and clinically insignificant prostate cancers using all histological thresholds on targeted biopsy using 4 targeted cores only compared to 6 targeted cores for the first targeted lesion.
- Detection rates for each randomised group of known prognostic risk categories. These are D'Amico, National Comprehensive Cancer Network (NCCN) and Cambridge Prognostic Groups (CPG).
- A comparison of the two MRI scoring systems, Likert and PIRADS [latest version as defined in MRI Reporting SOP], in terms of the proportion of patients biopsied and subsequently diagnosed with clinically significant and clinically insignificant prostate cancer, using each of the histological thresholds, on a prostate biopsy. Our study would be an opportunity to conduct a robust comparison of the two reporting systems in a large sample and allow inclusion in meta-analyses with studies that used either one alone.

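### Secondary definition (v) of clinically significant cancer is worded inconsistently in three places, and the section 2.4 version, read literally, leaves out Gleason >=4+3 cancers that the other two count

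*Protocol*

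**What the plan says.** Section 2.4 introduces five definitions to be used alongside the primary one ("we will also use the following histological thresholds"). The fifth is "Gleason 3+4=7 with >10% pattern 4 OR cribriform pattern OR a ductal component".

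Under the heading in section 5 on defining significance on histology, the corresponding item is "any amount of Gleason 3+4=7 with cribriform pattern or a ductal component or >/=10% pattern 4 or any Gleason >/=4+3".

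The Trial Summary, under secondary outcome measures, has "Gleason >/=3+4 [ISUP grade Group >/=2] with >/=10% pattern 4 OR presence of cribriform pattern OR presence of intraductal components".

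The histology paragraph in section 5 lists what the pathology report covers, including "percent pattern 4 and presence of cribriform pattern when Gleason 3+4, perineural invasion/lymphovascular invasion/intraductal components/neuroendocrine differentiation".

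Section 2.4 uses these thresholds for a stated endpoint: "The proportion of patients diagnosed with clinically significant and clinically insignificant prostate cancers using other histological thresholds". It uses them again to compare four with six targeted cores in the first lesion, to compare Likert with PIRADS, and in the analyses by centre.

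**The concern.** One endpoint definition should give one answer for each biopsy result. Here the section where a reader looks for endpoint definitions holds the version that differs most. It is tied to a single grade, Gleason 3+4=7, while definitions (i) to (iv) in the same list are all open upwards.

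A definition closed at the top is non-monotone: a worse cancer can count for less than a milder one. That matters most where the interventions may change the grade found, as with image-fusion against visual-registration or six cores against four. If better sampling reveals a higher grade in a man who already met (v), he leaves the significant group. Because the endpoint reports significant and insignificant cancers under each threshold, he also moves to the wrong side of the split.

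**Working it through.** The protocol states no figure for this definition, so the check is to apply the three wordings to the same biopsy results. The features in section 2.4 can be read in two ways: all tied to Gleason 3+4 (tied), or with cribriform and ductal standing alone as alternatives (free-standing).

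| Biopsy result | Trial Summary | Section 2.4 (v) | Section 5 |
|---|---|---|---|
| Gleason 4+3 or 4+4, no cribriform, ductal or intraductal feature | yes | **no** | yes |
| Gleason 4+3 or 4+4 with cribriform pattern | yes | **no** if tied, yes if free-standing | yes |
| Gleason 3+4, exactly 10% pattern 4, no other feature | yes | **no** | yes |
| Gleason 3+4, 5% pattern 4, intraductal only | yes | no | no |
| Gleason 3+4, 5% pattern 4, ductal only | no | yes | yes |

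Every pair of versions disagrees on at least one row, so these are three different rules. On grade and cut-off, section 2.4 is the outlier. On the feature, the Trial Summary is the outlier among the definitions, although its term is the one in the histology item list.

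**Direction of the error.** Take a man with Gleason 3+4, 20% pattern 4 and no other feature: section 2.4 counts him. Regrade him to 4+3 with 60% pattern 4 and no other feature: section 2.4 does not count him, while the other two versions do. If k men per 100 are upgraded in this way, the count under (v) falls by k x q. Here q is the fraction who met (v) before the upgrade and do not meet it after. For k = 5, the fall is at most 5 points, reached only if q = 1.

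**Size.** Let s be the share of Gleason >=3+4 cancers that are >=4+3. The documents do not give s; 25-50% is assumed here only to show the scale. Section 8.1 supplies the detection rates. Men affected per 100 = rate x s, which is an upper bound because the free-standing reading would keep some of them:

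- Randomisation 1: 38 x 0.25 = 9.5, to 38 x 0.50 = 19. On the 3230 men required before attrition: 3230 x 0.38 x 0.25 = 307, to 3230 x 0.38 x 0.50 = 614.
- Randomisation 2, visual-registration: 55 x 0.25 = 13.75, to 55 x 0.50 = 27.5.
- Randomisation 2, image-fusion: 65 x 0.25 = 16.25, to 65 x 0.50 = 32.5.

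**Can the sign reverse?** Use the tied reading and suppose, for simplicity, that every 3+4 cancer has a qualifying feature. With s = 25% in the visual-registration arm, (v) gives 55 x 0.75 = 41.25%. Image-fusion gives 65 x (1 - s), which falls below 41.25% once s exceeds 1 - 41.25/65 = 36.5%. A 10-point gain on the primary definition would then appear as a loss on (v). This shows that a reversal is arithmetically possible. It does not predict one.

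**The case against.** The strongest reply is that this is a drafting slip with little reach. Section 5 already prints the missing clause and cites a source, and the Trial Summary starts from Gleason >=3+4. An analyst who reads the whole protocol would probably reach the intended rule. The primary endpoint, "defined as any amount of Gleason >/=3+4 (ISUP Grade Group >/=2) on biopsy", does not use (v), nor does the sample size. Definitions (i) to (iv) all capture >=4+3, and (i) would show a shift to higher grades in the right direction. All of this stands, and it limits the severity. It does not remove the conflict, because any single rule adopted later must depart from at least two of the three wordings.

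A reader might also infer three stronger things that the documents do not support.

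- That section 2.4 excludes every Gleason >=4+3 cancer. This holds only if the features are tied to 3+4, which is the more natural reading. On the free-standing reading, >=4+3 cancers with cribriform or ductal features still count. So would a Gleason 3+3 cancer with a ductal component, which neither other version allows.
- That a ductal component cannot be derived from the trial data. The item list names "perineural invasion/lymphovascular invasion/intraductal components/neuroendocrine differentiation" and does not name ductal. But it refers to a Biopsy Reporting SOP and to other features, and neither the SOP nor the eCRF is shown. One can say only that the protocol's list does not name it.
- That a given upgrade rate translates one for one into a loss. As shown above, that is the maximum.

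**Conclusion.** The inconsistency is real and can be checked from the text alone. Section 2.4 differs from the other two versions on whether Gleason >=4+3 counts and on >10% against >=10%. Ductal and intraductal are used interchangeably across the definitions and the item list. Followed literally, section 2.4 misclassifies at least those >=4+3 cancers without cribriform or ductal features, and it makes the count under (v) fall when a man who met it is upgraded.

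The number affected cannot be stated from the documents, because it depends on the share of >=4+3 cancers. The figures above rest on an assumed 25-50% and are upper bounds. The consequence also requires that section 2.4 be applied as written.

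This should be fixed, as a secondary-endpoint matter. It is not a threat to the primary endpoint, the sample size or definitions (i) to (iv).

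**What to change.** Use one wording in the Trial Summary, section 2.4 and section 5:

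- Keep the explicit clause from section 5 that any Gleason >=4+3 qualifies. This also avoids relying on percent pattern 4 or cribriform status at higher grades, since the histology list mentions those two items in connection with Gleason 3+4.
- For Gleason 3+4, use the single cut-off of >=10% pattern 4, as in two of the three places, and punctuate so that it is plain which features qualify which grade.
- Choose one term, ductal or intraductal, that matches the item recorded under the Biopsy Reporting SOP and the eCRF. If ductal is kept, confirm that it is a recorded item and name it in the histology list.

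The cost is a text edit in three places and a check of the pathology form. No extra patients are needed. One histology item would be added only if ductal is kept and is not already collected. The change should be made before any outcome data by arm are seen, so that the choice of wording is prespecified.
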